Protocol Template Form

Item 1 UTHSCSA Tracking Number	HSC20120304H	Effect of mTOR Inhibition and Other Metabolism Modulating Interventions on the Elderly: Immune, Cognitive, and Functional Consequences
---------------------------------------	--------------	--

Item 2 Abstract / Project Summary	Provide a succinct and accurate description of the proposed research. State the purpose/aims. Describe concisely the research design and methods for achieving the stated goals. This section should be understandable to all members of the IRB, scientific and non-scientific. DO NOT EXCEED THE SPACE PROVIDED.
--	--

Purpose/Objectives: Several drugs, including rapamycin (RAPA), an inhibitor of the mTOR pathway, and acarbose (ACA), a metabolic modulator, have been shown to extend the lifespan in laboratory rodents and also delay or reverse certain age-associated functional deficiencies. However, the effects in older animals often differ from those in a younger cohort. In order to determine whether these drugs will enhance healthy aging in older human subjects, a series of pilot studies is proposed where the underlying mechanisms and outcomes will be assessed with the focus being on physiological systems known to decline with aging.

Research Design/Plan:

- [Sub-study A Rapamycin Alone](#), or
- [Sub-study B Acarbose followed by Rapamycin](#), or
- [Sub-study C Acarbose Alone](#), or
- [Sub-study D Rapamycin Alone – Cardiovascular Effects](#)

The effects of RAPA and/or ACA on cognitive, immune, physical, and other physiological systems known to be impacted with age will be investigated in a pilot study in a small number of elderly subjects. In the sub-studies using RAPA, a control group, matched for age and ethnicity, will be given a placebo (Sub-studies A&B; Sub-study D RAPA/no placebo). The study is designed such that a given subject will be enrolled in one of four sub-studies shown above as Sub-study A-D.

Methods: Subjects who meet the inclusion criteria and choose to participate in one of the sub-studies will be consented and will then undergo a set of standard tests to obtain baseline data on their current health status.

For Sub-study A Rapamycin Alone

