Subjects will receive Rapamycin or placebo for approximately two months. We will assess many parameters to assess changes due to the drug (RAPA), particularly in physiological systems known to change with aging, and will also measure indicators of health to ensure safe delivery of RAPA in the elderly cohort. Specifically, the tests to be run include the following: immune response to challenge with the trivalent seasonal influenza vaccine effects on the gut microbiome, perception of quality of life and depression, grip strength, timed walk, cognitive assessment, blood chemistry, immune and endocrine health, and other assessments of safe RAPA delivery. Some subjects may elect to participate in an optional imaging procedure to evaluate cerebral blood flow and metabolic rate of glucose using PET and MRI.

For Sub-study B Acarbose followed by Rapamycin

Subjects will receive ACA orally for approximately 2 months. The battery of tests outlined above (except immunization) will be performed at three time points (pre-ACA, after 2 months on ACA, and 1 month post-ACA termination), to measure the effects of ACA on the gut microbiome, basic blood metabolic markers, blood cell distributions, physical function parameters (including walking speed and grip strength), cognitive abilities, depression, cytokine levels, and blood cell function. ACA will be terminated and all subjects will be rested for approximately 1 month and will then enter the RAPA phase of study; they will be randomly assigned to either RAPA or placebo and will be maintained on the appropriate drug for a total of approximately 2 months. During that time, we will assess response to vaccine challenges and to other physiological measures, including those listed above. Subjects may also elect to participate in optional imaging procedures to evaluate cerebral blood flow and metabolic rate of glucose using PET and MRI.

For Sub-study C Acarbose alone

Subjects will be followed as in substudy B, but the tests will also be performed 1 month after termination of ACA.

For Sub-study D Rapamycin Alone – Cardiovascular Effects

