Aim I. Assess mTOR inhibition safety in elderly human subjects, 70-95 years of age.

Prior human studies of mTOR inhibition by RAPA have focused on subjects with underlying health issues (transplant recipients, patients with cancer or autoimmunity, etc.) so RAPA was often used in combination with other immunosuppressive or anti-proliferative drugs. Thus, we propose to assess whether RAPA can be safely delivered to an otherwise healthy, but elderly test population. Towards this end, subjects will be placed on mTOR inhibition by RAPA (Rapamune, Wyeth/Pfizer) and an equal number on placebo. Their health status will be assessed by: i) physical examination, ii) clinical blood work iii) weekly self-reporting of complications to the clinical nurse, and iv) use of both a depression scale and the SF36 questionnaire. Participants will remain on drug therapy (either Rapa or placebo) for the entire ~2 months of the RAPA study.

Aim II. Assess the effects of mTOR inhibition on vaccine efficacy in the elderly.

Humoral immune responses decline with advancing age in humans as evidenced by decreased vaccine efficacy and increased susceptibility to infection. Thus, to determine whether mTOR inhibition by RAPA alters the age-associated loss in immune competence, study participants will be immunized with the seasonal flu vaccine (subjects will not have had prior exposure to the composition used). Both humoral (antibody titer) and cellular (T cell proliferation) responses will be assessed. In addition, the subjects will receive a second immunization to test effects on memory B (antibody) and T cell responses.

Aim III. Determine whether mTOR inhibition can improve general immune features in the aged

mTOR inhibition's effects on immune parameters characteristically altered by aging will be assessed. These include: i) serum cytokine levels (IL-6, TGF- β , etc.) as indicators of increased inflammation, ii) the naive to memory T cell ratio that decreases with age due to thymus involution and memory expansion; and iii) T cell functional subsets as assessed by fluorescence-activated cell sorting (FACS) for cell surface markers and cytokine measures.

Aim IV. Determine whether mTOR inhibition can improve muscle strength and cognitive function

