
normal, healthy 70-95 years old; Veterans and non-veterans (All sub-studies)
 
In Sub-study D we will enroll males only, 70-95 years old, veterans and non-veterans.
	
 • Since this is a small pilot study, we have opted to limit subject heterogeneity by focusing on 70-95 years of age. • Subjects will be in good health with all chronic diseases (hypertension, coronary artery disease, etc.) clinically stable. Selected subjects will be in good health (Per the World Health Organization good health will be defined as complete physical, mental, and social well-being and not merely the absence of disease or infirmity. • For our purposes all diseases or infirmities will be clinically stable whether managed by medications or not. • All ethnicities will be included. • For cardiac and brain imaging by MRI, a pre-MRI screening questionnaire will be used to assess MRI safety and neurological health. 	
Exclusion criteria include:
 
 • Received current season influenza vaccine (exclusion for substudy A, B, C*; *NOT used in SubStudy D) • Diabetes, (*Substudy D - with A1c ≥ 6.5 or if treated with medication affecting glucose homeostasis History of skin ulcers or poor wound healing, • Smoking, • Liver disease, • Coumadin anti-coagulation, • treatment with drugs known to affect cytochrome P450 3A (diltiazem, erythromycin, etc) due to its role in RAPA metabolism • Treatment (>30days of therapy or long term) with a systemic immunosuppressant (prednisone, etc.) within the last year. • Patients with history of recent (within 6 months) Myocardial Infarction or active Coronary Disease. • Patients with history of recent (within 6 months) intestinal disorders • Exclusion criteria for MRI scan: known claustrophobia, metal implants in soft tissue of the body including pacemakers, aneurysm clips, ferrous metal fragments not anchored to bone (bullets, BBs, shrapnel, metal shavings), implanted medication pumps, and oral-facial metal appliances that are permanently secured but may result in low image quality. Participants may also be excluded for history of severe head trauma, brain injury, brain surgery, inflammation of the brain, or history of seizures.

Item 6

Research Plan / Description of the Research Methods a. Provide a *comprehensive narrative describing the research methods.*
Provide the *plan for data analysis* (include as applicable the *sample size calculation*).

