Step-by-Step Methods:**Methods for Sub-study A & B Rapamycin**

mTOR inhibition: Subjects will be randomized to mTOR inhibition by RAPA or placebo in equal sized groups. Those receiving the drug will be started on 1 mg per day with no loading dose. Dosage will be adjusted for a target whole blood concentration of 10-15 ng/ml and maintained there until the study's conclusion. RAPA blood levels will be determined by mass spec. The initial trough level will be drawn one week after initiation of therapy. When a maintenance dose is adjusted, the new dose will be maintained for 7 days before additional adjustments are made based on concentration monitoring. Reported adverse reactions to RAPA and related agents when used as solitary agents include mucositis, pneumonitis, skin rash, hyperlipidemia, hyperglycemia, thrombocytopenia, and anemia.

Clinical assessment: Subject health will be confirmed initially by history and physical exam, normal laboratory tests (fasting lipid profile, metabolic profile, CBC, and CK), and 12-lead EKG. Oral glucose tolerance test (OGTT): Baseline (fasting) samples for determination of glucose, insulin, and free fatty acid (FFA) concentrations will be drawn at -30, -15 and -0 min (these basal values are averaged). At time zero, each subject will ingest 75 g of glucose. Glucose, insulin and FFA are determined every 30 min for 2 h following glucose ingestion. The Matsuda index of insulin sensitivity will be calculated from OGTT results, as described (Matsuda and DeFronzo, 1999). At each visit, patients will receive a standard history, physical examination, blood chemistry assessment, and be queried in detail for RAPA adverse reactions including infections. A questionnaire (SF-36) designed to assess the benefits of health care interventions and the Geriatric Depression Scale questionnaire will allow us to characterize any adverse or beneficial effects. Between visits, subjects will be contacted weekly by the Clinical Nurse to ensure that no complications have arisen. Blood test for CK will be monitored.

If subjects have previously undergone all or part of screening labs/tests within the past 4 months, the data may be accepted for eligibility determination without screening labs or procedures having to be repeated.

Aim II. Assess the effects of mTOR inhibition on vaccine efficacy in the elderly.

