This is a pilot study designed to produce the data necessary for future larger studies. No data are currently available to guide sample size calculations.

OVERALL EXPERIMENTAL DESIGN The collection of samples and performance of procedures for Substudies A, B and C will typically be performed as indicated below**. Also, V1 may be combined with V0 if subject arrived fasting.

The collection of samples and performance of procedures for Substudy D will typically be performed as indicated in Table 2 on the following page.. However, at the discretion of the PI, some collections may be done at a visit before or after the one shown.

Table 1. Substudy A Rapamycin Only study visits 0, 1, 7-10; **Substudy B ACA+RAPA** study visits 0-10; **Substudy C ACA Only** study visits 0- 6 (as summarized in table below). **TABLE 1 DOES NOT APPLY TO SUBSTUDY D****

Visit number	V0	V1	V2	V3	1V4	1.5V5	2V6	3V7	4V8	5V9	6V10
Visit goal	Consent	Screening	Pre-ACA	ACA – 1 month	ACA – 6-7 wks	ACA ends	Post ACA2 month	termination	7 day RAPA	6 wks RAPA Safety	Imm
Study Phase	A,B,C	A,B,C	B,C	B,C	B,C	B,C	B,C	A,B	A,B	A,B	A,B
Week number (of phase) (time variable between visits 3 and 4)			0	4	6-7	48	12	0 (for RAPA)	1	6	8
Timing (days) – range				25-35 days after V2	38-45 days after V2	50-70 days after V2	25-35 days after V5	25-35 days after visit 2	6-9 days after V7	40-45 days after V7	13-15 days after v9
PROCEDURES											
Consent form	X			X							
EKG		X		X							
Physical exam & history; Safety measures: AE's and problems		X	X	X	X	X	X	X	X	X	X
Clinical blood tests, include:				X			X	X	X	X	X
Complete blood count		X	#			X	X	#	X	X	X
Metabolic profile		X	#			X	X	#	X	X	X
Fasting blood sugar; HbA1c		X	#			X	X	#	X	X	X
Fasting lipid profile		X	#			X	X	#	X	X	X
Urinalysis								x			x
OGTT		X			X		X		x	X	
Acarbose treatment begins			X		X						
Acarbose treatment ends						X	X				
RAPA or placebo begins								X	X		
SF-36 questionnaire			X		X	X	X	X	X		X
RAPA levels									X	X	X
Blood draw for lab, includes:				X			X	X	X		X
Cytokine profiles			X	X		X	X	X	X	X	X
Blood cell subsets by flow			X	X		X	X	X	X	X	X
T cell subsets			X	X		X	X	X	X	X	X
T cell proliferation to mitogen			X		X	X	X	X	X	X	X
Collect feces			X		X	X	X	X	X	X	X
Constipation Assessment			X	X	X	X	X	X	X	X	X
Immunizations: flu vaccine										X	X
T cell prolif to flu antigens									X	X	X
Antibody to flu antigens									X	X	X
Hand grip and 40 ft walk test*			X	X		X	X	X	X	X	X
Cognitive tests: EXIT/SLUMS and/or TAPS*			X	X		X	X	X	X		X

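### The abstract describes the Sub-study A and B placebo group as matched for age and ethnicity, but the methods give only randomization to equal-sized groups, with no balancing step and no age adjustment

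*Combined protocol and SAP*

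**What the plan says.** The abstract (Item 2, Research Design/Plan) says that in the RAPA sub-studies with a placebo, A and B, "a control group, matched for age and ethnicity, will be given a placebo".

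The text on allocation reads differently:

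- Item 6, Methods for Sub-study A & B: "Subjects will be randomized to mTOR inhibition by RAPA or placebo in equal sized groups".
- Item 2, Sub-study B: after the acarbose phase and rest period, "they will be randomly assigned to either RAPA or placebo".
- Item 4, Aim I: subjects on RAPA and "an equal number on placebo". This gives the ratio only.

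None of these names a stratification factor, block, minimization rule, pairing rule, age band or set of ethnic categories.

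Eligibility (Item 5) does not create a match. On age, "we have opted to limit subject heterogeneity by focusing on 70-95 years of age", which still leaves a 25-year span. On ethnicity, "All ethnicities will be included".

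On size, the abstract describes work "in a pilot study in a small number of elderly subjects", and the Data Analysis Plan says "No data are currently available to guide sample size calculations". No number is given for Sub-study A or B.

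On analysis, Item 6 (Aim IV) plans before/after comparisons and comparisons within and between the RAPA and placebo groups. Aim III compares immune measures with their pre-treatment levels. Adjustment for age or ethnicity is not mentioned.

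**The concern.** Matching is a design property that a reader will rely on. Someone who reads only the abstract, or a later report that repeats it, will take it that the arms were made alike in age and ethnicity. The methods contain nothing that would make them so.

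Age matters here more than in most trials. The immune parameters, grip strength, walking speed and cognition are studied because they decline or change with age. The protocol also suggests that the response itself may depend on age: Item 4 says vaccine efficacy falls with age, and Item 3 suggests that the over-85s may benefit more from RAPA than younger people. If one arm happens to be older, part of the observed difference in such outcomes may be due to age. With no age term in the analysis, that part is neither removed nor shown.

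At stake are the precision of the between-arm estimates, which are meant to inform a larger trial, and the accuracy of the description of the control group.

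**Working it through.** The plan states no sample size, power or balance figure for Sub-studies A and B, so there is none to reproduce. The check asks how often unrestricted 1:1 randomization would leave a visible age gap.

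**Inputs**

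- Allocation: random, equal-sized groups (Item 6).
- Age range: 70-95 years (Item 5).
- Subjects per arm, *n*: not stated. Assumed 6, 10 and 15.
- Age SD, *s*: not stated. Assumed 5 to 7 years. For scale, a uniform spread over 70-95 has SD 25/√12 = 7.2.
- Gap of interest: 3 years. This is an illustrative cut-off, not one taken from the plan.

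**Formula**

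SD of the difference in mean age = *s* × √(2/*n*).

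P(|difference| > 3) = 2 × [1 − Φ(3 / that SD)].

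**Results**

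| *n* per arm | SD of difference, *s* = 5 | SD of difference, *s* = 7 | 3/SD | P(gap > 3 years) |
|---|---|---|---|---|
| 6 | 2.89 | 4.04 | 1.04 to 0.74 | 30% to 46% |
| 10 | 2.24 | 3.13 | 1.34 to 0.96 | 18% to 34% |
| 15 | 1.83 | 2.56 | 1.64 to 1.17 | 10% to 24% |

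The same formula gives 6% to 18% at 20 per arm and 2% to 10% at 30. The point therefore weakens quickly once the arms are larger than a small pilot would have.

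**Check with a different threshold.** A gap of at least half an SD needs no assumed SD: P = 2 × [1 − Φ(0.5/√(2/*n*))]. This gives 39% at 6 per arm, 26% at 10, 17% at 15, 11% at 20 and 5% at 30.

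**Effect on an outcome.** If an outcome changes by *b* units per year of age, a 3-year gap moves the unadjusted arm difference by 3*b*. For a change-from-baseline analysis, *b* is the effect of age on the two-month change, which may be much smaller than its effect on the level. The documents give no value of *b*, so the shift cannot be sized.

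**The case against.** **The two statements can both be true.** Stratified or matched-pair randomization gives arms that are randomized and also alike on the chosen factors, and the methods do not say that randomization is simple. This stands. A reader might infer that the abstract and methods contradict each other and cannot both be followed. The documents support only a weaker statement: the abstract claims a property and no section says how it is obtained.

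**Nothing suggests that controls are picked by hand.** A reader might infer that staff choose controls to fit, which would make allocation predictable. The text on allocation says random, so there is no basis for that.

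**Chance imbalance is not bias.** Under randomization an age gap is random error, already reflected in the standard error. Calling it confounding, in the sense of systematic error, would be wrong. The plan also uses each subject's own baseline, and for the vaccine response it says it does so because subjects differ. Both points stand. They reduce the consequence but do not make the arms matched. Nor does a baseline comparison remove any effect of age on the change itself.

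**Not every outcome is age-driven.** Aim I concerns safety, and the glucose tolerance test was added because of hyperglycemia reported in transplant patients. The point is confined to the immune, physical and cognitive outcomes.

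**The probabilities rest on assumptions, and an ethnicity figure can mislead.** With half of all subjects in one ethnic group, the chance of a gap of at least 30 percentage points is 57% at 6 per arm. But the smallest possible non-zero gap there is 4 versus 2, or 33 points, so the 57% only says that the split is not exactly 3 versus 3: 1 − (20 × 20)/924 = 0.57. At 10 per arm the figure is 18%. The conclusion should not rest on ethnicity.

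**Conclusion.** The point holds as a mismatch between a stated design property and the methods, with a modest statistical cost. Neither the allocation text nor the analysis text delivers or protects an age match in Sub-studies A and B. If allocation is unrestricted, a mean age gap of more than 3 years is quite likely at 6 per arm (30-46%) and far from rare at 15 (10-24%), given an age SD of 5 to 7 years. Arm sizes, SD and cut-off are all assumptions, so these figures are illustrative; at 30 per arm the concern largely fades.

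It would go too far to read this as a biased comparison or a broken randomization. The RAPA-placebo comparison is unbiased on average. What is lost is precision on age-related outcomes, together with the right to describe the controls as matched.

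The change is worth making: age is already recorded, and balancing on it and adjusting for it are cheap.

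**What to change.** 1. **Allocation (Item 6, Methods for Sub-study A & B).** State that subjects are randomized by minimization with a random element, or in stratified blocks, on age band (for example 70-79 and 80-95). Add ethnicity only if numbers allow: the documents define no ethnic categories, and crossing several factors at 6 to 15 per arm would leave sparse strata.
2. **Analysis (Item 6, Data Analysis Plan, and Aims II to IV).** Prespecify that RAPA-placebo comparisons are adjusted for age and the outcome's baseline value.
3. **Abstract (Item 2).** Describe the control group as randomized and balanced for age, adding ethnicity only if it is a balancing factor.
4. **If no balancing is done.** Delete the word *matched*, describe the control group simply as randomized, and keep the age adjustment.

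The cost is a revised randomization list or a short minimization program, slightly more allocation administration, a few sentences of text, and one or two degrees of freedom in a small sample. Age and ethnicity can both be recorded by screening, so no new data collection is needed. Sub-studies C and D need no change.

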--	--

Item 5 Study Population(s) Being Recruited
 
In your recruitment plan, how many different populations of prospective subjects do you plan to target? Provide number: 1
	
Identify the criteria for inclusion:
	
Identify the criteria for exclusion:

---	--	--

e.g., a population can be individuals with type 2 diabetes controlled with diet and/or a population of healthy controls. Or a population can be individuals attending an education program, etc.
 
List each different population on a separate row and provide a short descriptive label: (e.g., normal-healthy, diabetics, parents, children, etc.)
 
To add rows use copy & paste
		

normal, healthy 70-95 years old; Veterans and non-veterans (All sub-studies)
 
In Sub-study D we will enroll males only, 70-95 years old, veterans and non-veterans.
	
 • Since this is a small pilot study, we have opted to limit subject heterogeneity by focusing on 70-95 years of age. • Subjects will be in good health with all chronic diseases (hypertension, coronary artery disease, etc.) clinically stable. Selected subjects will be in good health (Per the World Health Organization good health will be defined as complete physical, mental, and social well-being and not merely the absence of disease or infirmity. • For our purposes all diseases or infirmities will be clinically stable whether managed by medications or not. • All ethnicities will be included. • For cardiac and brain imaging by MRI, a pre-MRI screening questionnaire will be used to assess MRI safety and neurological health. 	
Exclusion criteria include:
 
 • Received current season influenza vaccine (exclusion for substudy A, B, C*; *NOT used in SubStudy D) • Diabetes, (*Substudy D - with A1c ≥ 6.5 or if treated with medication affecting glucose homeostasis History of skin ulcers or poor wound healing, • Smoking, • Liver disease, • Coumadin anti-coagulation, • treatment with drugs known to affect cytochrome P450 3A (diltiazem, erythromycin, etc) due to its role in RAPA metabolism • Treatment (>30days of therapy or long term) with a systemic immunosuppressant (prednisone, etc.) within the last year. • Patients with history of recent (within 6 months) Myocardial Infarction or active Coronary Disease. • Patients with history of recent (within 6 months) intestinal disorders • Exclusion criteria for MRI scan: known claustrophobia, metal implants in soft tissue of the body including pacemakers, aneurysm clips, ferrous metal fragments not anchored to bone (bullets, BBs, shrapnel, metal shavings), implanted medication pumps, and oral-facial metal appliances that are permanently secured but may result in low image quality. Participants may also be excluded for history of severe head trauma, brain injury, brain surgery, inflammation of the brain, or history of seizures.

Item 6

Research Plan / Description of the Research Methods a. Provide a *comprehensive narrative describing the research methods.*
Provide the *plan for data analysis* (include as applicable the *sample size calculation*).

Step-by-Step Methods:**Methods for Sub-study A & B Rapamycin**

mTOR inhibition: Subjects will be randomized to mTOR inhibition by RAPA or placebo in equal sized groups. Those receiving the drug will be started on 1 mg per day with no loading dose. Dosage will be adjusted for a target whole blood concentration of 10-15 ng/ml and maintained there until the study's conclusion. RAPA blood levels will be determined by mass spec. The initial trough level will be drawn one week after initiation of therapy. When a maintenance dose is adjusted, the new dose will be maintained for 7 days before additional adjustments are made based on concentration monitoring. Reported adverse reactions to RAPA and related agents when used as solitary agents include mucositis, pneumonitis, skin rash, hyperlipidemia, hyperglycemia, thrombocytopenia, and anemia.

Clinical assessment: Subject health will be confirmed initially by history and physical exam, normal laboratory tests (fasting lipid profile, metabolic profile, CBC, and CK), and 12-lead EKG. Oral glucose tolerance test (OGTT): Baseline (fasting) samples for determination of glucose, insulin, and free fatty acid (FFA) concentrations will be drawn at -30, -15 and -0 min (these basal values are averaged). At time zero, each subject will ingest 75 g of glucose. Glucose, insulin and FFA are determined every 30 min for 2 h following glucose ingestion. The Matsuda index of insulin sensitivity will be calculated from OGTT results, as described (Matsuda and DeFronzo, 1999). At each visit, patients will receive a standard history, physical examination, blood chemistry assessment, and be queried in detail for RAPA adverse reactions including infections. A questionnaire (SF-36) designed to assess the benefits of health care interventions and the Geriatric Depression Scale questionnaire will allow us to characterize any adverse or beneficial effects. Between visits, subjects will be contacted weekly by the Clinical Nurse to ensure that no complications have arisen. Blood test for CK will be monitored.

If subjects have previously undergone all or part of screening labs/tests within the past 4 months, the data may be accepted for eligibility determination without screening labs or procedures having to be repeated.

Aim II. Assess the effects of mTOR inhibition on vaccine efficacy in the elderly.

Rationale: One serious consequence of immune senescence is the age-associated loss of responsiveness to immune challenges. When examined in humans, mTOR inhibition by RAPA did not appear to decrease vaccine efficacy, but this is difficult to conclude given that these subjects were on combination therapies for serious underlying health issues (recent transplant or cancer). Thus, using the cohort described in Aim I, we have a unique opportunity to ask whether mTOR inhibition by RAPA will enhance immunity in otherwise clinically stable elderly individuals.

Immunization: We chose a vaccine that is commonly given to the elderly and was previously reported to show small improvements in a study of mTOR inhibition in adults performed by Novartis (Mannick, et al.). The study will be timed such that none of our subjects will have already been immunized with that season's trivalent influenza vaccine although it is likely that they will have been previously immunized with other flu variants and/or previously had flu infections. We will compare pre-immune and post-immune data to control for the heterogeneity in the population. Typically, the seasonal flu vaccine contains three different influenza viruses determined each year by the CDC based on variants predicted to dominate in the US during. A flu shot is considered standard of care for individuals in this age group and the composition used will be the one recommended by the VA; it is approved for humans. Standard adult dosing of Trivalent influenza vaccine will be initiated 1½ months after RAPA treatment begins and it will be given only once, as recommended.

Outcome measures and expected results: Subjects will return to the clinic for blood collection as indicated on Figure 2; both humoral (antibody titer) and cellular (T cell proliferation) responses to influenza antigens will be assessed. Effects of mTOR inhibition by RAPA on B cell responses: Following each immunization (at day 7 and 14), 5 ml of blood will be collected and serum prepared. The titer of anti-flu virus antibodies in these specimens will be determined by ELISAs using standardized kits (Alpha Diagnostics Inc). If our hypothesis were correct, the primary responses would be low in these elderly subjects with higher levels in individuals on RAPA.

Effects of mTOR inhibition by RAPA on influenza virus-specific T cells: Age associated deficiencies are also seen for cellular (T-cell mediated) responses. This is likely due to a loss of naïve T cell production (a consequence of thymus involution), coupled with an increase in memory T cells due to antigenic exposure. Thus, it is also critical to ask whether RAPA will compensate for losses in T cell immunity with age. Towards this end, 25 ml blood will be collected 7 days

after each immunization. Peripheral blood mononuclear cells (PBMCs) will be harvested and stimulated *in vitro* in triplicate with serial dilutions of recombinant flu viral antigens or with control stimuli [PHA or anti-CD3/CD28 (positive controls) and vehicle (negative control)]. Proliferation and cytokine production in response to the test stimulus are measured to determine both the extent of T cell activation and the nature of the T cell response (i.e. T_H1, T_H2, T_H17). The effects of mTOR inhibition on T cell maturation in response to an immune challenge have not been rigorously investigated and have never been tested in elderly humans. If our hypothesis were correct, RAPA would enhance antigen-specific T cell proliferation while suppressing overall proliferation to PHA or anti-CD3/CD28 stimuli.

Aim III. Determine whether mTOR inhibition can improve general immune features in the aged

Rationale The effects of mTOR inhibition are pleiotropic and the consequences of treatment may be different in young immunologically-competent individuals than in elderly subjects with age-associated immune dysfunctions (Fig. 1). Thus, we will examine several parameters of immune health in the mTOR inhibition by RAPA and placebo controlled subjects to assess whether the drug has mitigated the effects of aging. Importantly, we will be able to correlate improved humoral responses (Aim II) with changes in specific immune parameters measure in Aim III.

Immune parameters assessed and expected results We will focus on parameters known to change with age (Table 1) using blood collected after approximately 1, 6, and 8 weeks on RAPA or placebo, the following will be assessed and compared to levels determined prior to initiation of the treatment: i) Serum cytokine levels; Luminex-based assays will be used; these allow simultaneous measurement of 28 different cytokines. It is expected that RAPA will have the beneficial effect of decreasing the levels of pro-inflammatory cytokines (TGF- β , IL-12, IL-6, TNF- α). ii) Naive T cells are lost with aging due to thymus involution and a lifetime of clonal expansion of memory T cells. In mice, RAPA appears to protect these naive T cells which could then allow for a healthier immune response to “new” antigens in older individuals. To assess whether the same is seen in humans, PBMCs will be analyzed by FACS to assess the proportion of memory vs. naive T cells both before and after RAPA treatment. iii) T cell functional subsets will be assessed by FACS for cell surface markers and intracellular cytokines. Although expectations are less clear here, it will be important to assess whether RAPA has effects on human T cell development that are analogous to those seen in rodents. Moreover, these measurements have not previously been ascertained for human subjects in this advanced age group.

Aim IV. Determine whether mTOR inhibition can improve muscle strength and cognitive function

The following tests will be performed to assess RAPA affects on physiological parameters:

- 1) Grip strength (3 consecutive measurements by grip-strength dynamometer): participants will be seated in a chair with the forearm at a 90° elbow bend and 3 consecutive grip strengths will be completed with a standard grip strength dynamometer (in Kg) for the dominant hand. Results will be averaged for analysis.
- 2) Timed 40-foot walk: each participant will perform 3 walks (timed with a stopwatch) at their preferred walking speed over a measured 40-foot path. Results will be averaged for analysis.

Statistical comparisons will be made between measurements made before and after, as well as both within and between mTOR inhibited and placebo groups to test our hypothesis.

Cognitive assessment: All subjects will undergo cognitive assessments within one week of their recruitment (before treatment) and at the end of treatment (approximately 2 months after entering the RAPA phase of the study). The cognitive tests will be selected from a battery of the following validated tests – EXIT, SLUMS, and/or TAPS – with care taken to avoid use of ones employed in the ACA phase (as appropriate) to limit the effects of “learning/memory”.

Results of the foregoing (grip strength, timed walk, and cognitive assessment scores) will be compared between groups.

Aim V. Assess the effects of RAPA on the gut microbiome.

Rationale Composition of the gut microbiota is known to change with age and this most likely contributes to increases in inflammation seen in older individuals. Given its broad effects on metabolic regulation and its oral delivery route, RAPA is likely to alter the gut microbiome and may thereby elicit changes in the host immune system (addressed in Aims II and III). In order to address this possibility, we will collect fecal specimens from the RAPA and placebo treated subjects at 4 time points, prior to RAPA treatment and after 1, 6, and 8 weeks on the drug. The gut microbiome will be characterized initially from the pre-treatment and 8 week treatment samples. The other fecal specimens will be stored for future analysis of the kinetics of interesting changes observed.

Approach The advent of next generation DNA sequencing has revolutionized efforts to characterize the endogenous microbiome. An oral medication, like RAPA, will likely target the gut microbiome. Thus, subjects will self-collect feces in sterile containers and deliver it to the clinic at their regular visits. DNA isolation will be performed by the Genomics Core facility on a fee-for-service basis and the samples will be delivered to the Sequencing Core Facility for analysis. The bacterial rDNA in each fecal sample will be amplified using primers from conserved regions of the 16S ribosomal RNA genes. Amplified DNAs are then used to generate a library which is subsequently subjected to deep (next gen) sequencing.

Sub-study B & C Acarbose

